## **3. STUDY CONDUCT**

### **3.1 RANDOMIZATION**

Patients will be enrolled to receive Mircera once every 4 weeks, and no randomization will be performed. An interactive voice or Web-based response system (IxRS) will be used to track the enrollment and to monitor the disposition of patients with respect to the different subgroups (age group and dialysis type).

### **3.2 DATA MONITORING**

The IMC reviewed the general safety and efficacy of Mircera in this patient population as well as PK data on 12 September 2019, after 12 subjects completed the core study period (20 weeks of treatment). The IMC consisted of representative(s) from Clinical Science, Drug Safety, Clinical Pharmacology and Biostatistics. The main purpose of the IMC was to assess if the conversion factor from the previous ESA dose to give the starting dose of Mircera SC is appropriate to maintain stable hemoglobin (Hb). The SMT

was recommended to plan and prepare for this interim analysis. The SMT Statistician and the Statistical Programming Analyst performed the interim analyses. Based on the review of the data and the meeting discussion, the IMC recommended to continue the study unchanged. The Development Review Committee (DRC) chair, on behalf of the study team, accepted the IMC recommendations. For detailed description of the role and process of the IMC, please refer to the IMC Agreement.

#### **4. STATISTICAL METHODS**

##### **4.1 ANALYSIS POPULATIONS**

###### **4.1.1 Intent to Treat (ITT) Population**

The Intent to Treat (ITT) population consists of all patients enrolled in the study.

###### **4.1.2 Per Protocol Population**

The Per-Protocol (PP) population is defined as all patients included in the safety population and who have no major protocol deviations as defined below.

1. Patients with less than 3 Hb values during the evaluation period.
2. Patients who miss any application of study medication at week 13 or week 17.
3. Patients with an overdose of Mircera at week 17 captured as a protocol deviation
4. Patient with wrong Mircera starting dose
5. Patients who do not fulfill the inclusion criteria for:
  - hemoglobin
  - iron levels
  - stable dose and dosing interval of SC treatment with epoetin alfa, epoetin beta or biosimilars, or darbepoetin alfa
6. Patients who fulfill any of the exclusion criteria:
  - Hemolytic anemia
  - Use of prohibited therapy

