4.5.6.1 Safety Assessments

Normal ranges for the study laboratory parameters should be supplied to Roche before the study starts. Blood sampling should always be performed before ESA administration and for patients on HD before the dialysis. The following laboratory assessments will be performed throughout the study at selected visits (see the schedules of activities in [Appendix 1](#) and [Appendix 2](#)) and analyzed at the study site's local laboratory:

- Hematology: Hb, RBC, absolute reticulocyte count
- Safety laboratory: leukocytes plus differential, AST, ALT, serum albumin, ALP, C-reactive protein, potassium, phosphorus, calcium, and platelets
- Serum creatinine: measured only for patients not on dialysis
eGFR will be calculated using the Bedside Schwartz formula (see [Appendix 3](#)).

- Iron parameters: serum ferritin, serum iron, and TSAT. TSAT will be calculated as described in [Appendix 3](#) with either serum transferrin or total iron-binding capacity. The percentage of hypochromic red blood cell may be determined instead of TSAT.
- Serum pregnancy test for post-pubertal female patients of childbearing potential
- Kt/V for patients on PD
 - Frequency will follow current Kidney Disease Outcomes Quality Initiative (KDOQI) guidelines (2006).
- Kt/V or URR for patients on HD
 - Frequency will follow current KDOQI guidelines (2006).

Per individual, the trial-related blood loss (including any losses in the maneuver) should not exceed 3% of the total blood volume during a period of four weeks and should not exceed 1% at any single time. The total volume of blood is estimated at 80 to 90 ml/kg body weight; 3% is 2.4 ml blood per kg body weight (DG SANTE 2008). Blood sampling to assess the different laboratory parameters should be done routinely at the site but should not exceed the recommended maximal volume of 2.4 ml per kg per four weeks.

Samples for the following laboratory tests will be sent to one or several bioanalytical laboratories for analysis:

- Serum samples will be collected to evaluate the pharmacokinetics of Mircera administered subcutaneously (see Section [4.5.6.2](#)).
- Anti-EPO and anti-Mircera antibody will be determined at Week 1, Visit 3, at Week 9 (Visit 6), and follow-up visit (Week 21, Visit 10). An additional sample will be collected at Week 45 (Visit 16) for the patients participating in the safety extension period.

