#### **4.3.1 Primary Efficacy Endpoint**

Hb concentration values (g/dL) over time and change in Hb from baseline to evaluation period will be presented in summary tables and graphically. The estimates will be summarized descriptively using means, standard deviation and percentiles.

The individual change from baseline will be reported using summary statistics (including mean, standard deviation and 90% CI of mean change). No formal statistical testing will be performed. Additional analysis will be performed by age category (<5, 5-11, ≥12 years), dialysis type (not yet on dialysis, PD, HD) and previous ESA (epoetin [epoetin alfa or epoetin beta or biosimilar] or darbepoetin alfa), if numbers allow.

The 90% confidence interval (CI) for the average per-patient Hb change from baseline to the evaluation period (weeks 17-21) will be calculated. If the lower limit of the CI is ≥-1 g/dL, the upper limit ≤1 g/dL and the number of dose increases and decreases are approximately balanced across the patients the conversion factor from prior ESA treatment for the first Mircera dose will be considered appropriate.

The Hb change from baseline is calculated on a per-patient basis, using an Area Under the Curve (AUC) approach to calculate an individual's average for both the baseline and evaluation periods and taking the difference. This per-patient change is then averaged over all patients and the confidence interval calculated.

The baseline period is defined as all assessments between the day of first study dose and the previous 35 days. If during the baseline period Hb measurements  $H_0, \dots, H_n$  are taken at timepoints  $t_0, \dots, t_n$ , a time adjusted average baseline Hb value will be calculated by

$$y = \frac{1}{2(t_n - t_0)} \sum_i (H_i + H_{i-1})(t_i - t_{i-1})$$

The value on the day of the first dose is included in the baseline calculation, as this assessment will be performed before the first dose is given.

The average Hb value for each individual during the evaluation period will be calculated using the same method as for the baseline period. The evaluation period is defined as all assessments between Visit 8 (Week 17) and Visit 10 (Week 21) inclusive. Subtracting the baseline period value from the evaluation period value gives the change in Hb concentration (g/dL) between the baseline and evaluation period.

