- b Visit window  $\pm 3$  days. All study visits should be scheduled based on the date of the first Mircera dose at Visit 3 (Week 1). For patients under HD or patients converting to HD, the study visits should occur on the day of the mid-week dialysis.
- c Mircera is administered every 4 weeks during dose titration and evaluation periods.
- d Follow-up visit assessments should be performed before resuming *epoetin alfa*, *epoetin beta*, or *darbepoetin alfa* dose.
- e Medical history includes demographics, other diseases, etiology of CKD, details of dialysis, previous treatments including ESA treatments, and iron supplementation.
- f Includes evaluation of the head, eyes, ears, nose, and throat, and the cardiovascular, dermatologic, musculoskeletal, respiratory, gastrointestinal, genitourinary, and neurologic systems. Any abnormality identified should be recorded on the corresponding page of the eCRF.
- g Serum pregnancy test should be performed in post-pubertal female patients of childbearing potential. If a pregnancy is suspected, the serum pregnancy test must be repeated during the course of the study.
- h Systolic and diastolic blood pressure and pulse rate will be recorded while the patient is if possible in a seated position, and they will be measured before blood sampling. The blood pressure should be measured at least twice and the average of these measurements should be recorded. An appropriate-sized cuff should be used. Blood pressure should be determined before and after the dialysis session for patients with HD. Body weight will also be recorded (after dialysis for patients on HD).
- i Includes Hb, RBC, and absolute reticulocyte count. Samples should always be obtained on the same day of the week, if possible, prior to injection of Mircera and, for patients on HD, before dialysis.

- 
- j Serum creatinine should be measured only for patients not on dialysis. eGFR will be calculated using the Bedside Schwartz formula (see Appendix 3 of protocol).
  - k Includes serum ferritin, serum iron and TSAT. TSAT will be calculated as described in Appendix 3 of protocol with either serum transferrin or total iron-binding capacity. The percentage of hypochromic red blood cells may be determined instead of TSAT.
  - l Includes leukocytes plus differential, AST, ALT, serum albumin, ALP, C-reactive protein, potassium, phosphorus, calcium, and platelets.

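### The per-protocol set excludes an overdose at Week 17 but not at Week 13, although missed doses count at both visits and the Week 13 dose precedes every scheduled evaluation Hb

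*SAP*

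**What the plan says.** SAP section 4.1.2 starts from the safety population and keeps patients "who have no major protocol deviations as defined below". Four of its six criteria bear on this point:

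- Criterion 1 removes "Patients with less than 3 Hb values during the evaluation period".
- Criterion 2 removes "Patients who miss any application of study medication at week 13 or week 17".
- Criterion 3 removes "Patients with an overdose of Mircera at week 17 captured as a protocol deviation".
- Criterion 4 removes a "Patient with wrong Mircera starting dose".

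For the endpoint, SAP section 4.3.1 states: "The evaluation period is defined as all assessments between Visit 8 (Week 17) and Visit 10 (Week 21) inclusive". The schedule in SAP Appendix 2 puts hematology at Weeks 17, 19 and 21 of that window, and Mircera at Weeks 1, 5, 9, 13 and 17.

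On the order of events on a dosing day, Protocol section 4.5.6.1 says: "Blood sampling should always be performed before ESA administration and for patients on HD before the dialysis". Footnote i of SAP Appendix 2 likewise places the hematology sample "prior to injection of Mircera and, for patients on HD, before dialysis".

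Protocol section 6.4 describes the per-protocol analysis as additional and leaves its exact definition to the SAP. Protocol section 6.4 and SAP section 4.3 both assign the primary and secondary efficacy analyses to the ITT population.

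**The concern.** Naming Weeks 13 and 17 for missed doses suggests that the SAP sees both doses as relevant to the evaluation period. For too much drug it names only the later dose, and it does not say why. Because Hb is sampled before dosing, the dose left out is the one that comes before every scheduled evaluation reading.

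At stake is how cleanly the per-protocol estimate can be read. That set is meant to show the Hb change in patients dosed as planned. As written, it can include a patient whose evaluation Hb partly reflects a Week 13 dosing error, a kind of contamination that the list already guards against for missed doses.

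**Working it through.** The plan attaches no figure to this point. The check sets the criteria against the schedule and then applies the SAP's own averaging formula.

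**1. Is a Week 13 overdose caught elsewhere?** The list is closed. Criterion 4 reaches only the Week 1 dose. Criteria 1, 2, 5 and 6 concern the number of Hb values, missed doses, three inclusion criteria, and hemolytic anemia or prohibited therapy. None covers a Week 13 overdose.

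**2. Which readings follow which dose?** Doses are four weeks apart and Hb is drawn first on a dosing day.

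- Week 13 dose: precedes the Hb at Weeks 17, 19 and 21, so 3 of 3.
- Week 17 dose: precedes the Hb at Weeks 19 and 21, so 2 of 3.

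These counts refer to scheduled visits. The evaluation period takes in every assessment, so unscheduled values could change them.

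**3. What weight do those readings carry?** With three values at times t0, t1, t2 and T = t2 − t0, the trapezoid average in SAP section 4.3.1 gives these weights:

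- first value: (t1 − t0) / (2T)
- second value: (t2 − t0) / (2T) = 1/2
- third value: (t2 − t1) / (2T)

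For days 0, 14 and 28 they are 14/56, 28/56 and 14/56, that is 0.25, 0.50 and 0.25. The Week 13 dose precedes 100% of the weight. The Week 17 dose precedes 0.50 + 0.25 = 75%.

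The visit window is ±3 days. Moving only the Week 19 visit gives 1 − 17/56 = 70% to 1 − 11/56 = 80%. Moving all three visits against each other gives 1 − 20/56 = 64% (days −3, 17, 25) to 1 − 8/56 = 86% (days 3, 11, 31). The Week 13 figure stays at 100%.

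**4. Could a Week 13 overdose still show at Weeks 17 to 21?** Protocol section 1.2 gives a subcutaneous half-life of about 130 hours. Four weeks is 672 hours, and 672/130 = 5.2 half-lives, which leaves about 2.8% of the drug. Carry-over would therefore run mainly through Hb already produced. That is plausible, because Protocol section 6.7 describes the existing Hb model as a life-span model. The documents do not quantify it.

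**5. How far could one such patient move the mean?** This step rests on assumptions. The number of patients is 40 × 0.70 = 28, from the planned enrollment and the assumed 30% withdrawal. The shift d in one patient's whole time-averaged evaluation Hb is not in the documents and is varied from +1 to +3 g/dL. The mean moves by d/28:

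- d = 1: 1/28 = 0.04 g/dL
- d = 2: 2/28 = 0.07 g/dL
- d = 3: 3/28 = 0.11 g/dL

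For scale, with the planning SD of 1.5 the half-width of a 90% CI at n = 28 is 1.703 × 1.5/√28 = 0.48 g/dL. A per-protocol set smaller than 28 would raise the shift in proportion to 1/n.

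**The case against.** The strongest reply is that counting readings after a dose says nothing about the size of an effect. By the same count, overdoses at Weeks 5 and 9 also score 100%. That stands. What singles out Week 13 is criterion 2, which already treats it as relevant.

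A reader might go further and infer that the set drops the less affected patients and keeps the more affected ones. The documents do not support that. Little of a Week 13 dose remains by Week 17, whereas a Week 17 overdose has its exposure inside the evaluation window. Under Protocol section 4.3.2.1.1 the Week 17 dose may be adjusted on that day's Hb, so a Week 13 effect can be partly offset. After Week 17 no further dose is scheduled before the Week 21 reading. Against this, Hb already produced may persist. The relative size is open in both directions.

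Missed doses and overdoses are also different deviations. Missing Week 13 leaves eight weeks between doses, while Protocol section 5.4.4 counts any accidental excess over the assigned dose as an overdose, however small. Identical windows are therefore not a logical necessity. This is a possible rationale, but the SAP does not state it.

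Finally, a Week 13 overdose would not be invisible. Protocol section 5.4.4 requires it to be recorded, and SAP section 4.2 has major deviations listed and assessed for their effect on interpretation. That reduces the consequence but does not change who is in the set.

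**Conclusion.** The point holds as an unexplained inconsistency in the definition of a supportive analysis set. A Week 13 overdose precedes all three scheduled evaluation readings and does not exclude the patient; a Week 17 overdose precedes two and does.

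The likely effect is small. One retained patient would move the mean by 0.04 to 0.11 g/dL under the assumed shifts, and the documents give no expected frequency of overdoses.

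Two stronger readings should be resisted. One is that the gap defeats the purpose of the per-protocol set: it concerns one type of deviation at one visit, and the other criteria are unaffected. The other is that it threatens the trial's conclusion on the conversion factor. That criterion sits in SAP section 4.3.1 within the primary analysis, which uses the ITT population, so per-protocol membership does not alter it.

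The conclusion assumes that sampling and dosing follow the schedule and that no unscheduled Hb values enter the evaluation period.

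**What to change.** Add Week 13 to criterion 3 of SAP section 4.1.2, so that an overdose recorded as a protocol deviation at either Week 13 or Week 17 excludes the patient, matching the two visits in criterion 2. If the difference is intended, one sentence giving the reason would serve instead. Either should be settled before the database is locked.

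The cost is a few words and no new data collection. The only downside is a per-protocol set that may be slightly smaller. The change concerns the analysis set alone and leaves dosing untouched.

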###### **4.1.3 Safety Population**

The safety analysis population consists of all patients who received at least one dose of study drug regardless of whether they withdrew prematurely or not.

##### **4.2 ANALYSIS OF STUDY CONDUCT**

The summary of patient disposition will give a breakdown of the number and percentage of patients who: enrolled; started, discontinued (with reasons for discontinuation) and completed the core study and the safety extension period.

Premature withdrawals will be listed and summarized by age category and dialysis category.

Patients completing 20 weeks of treatment (having returned for an assessment at study week 21) as defined in the protocol as a key cut-point will also be summarized.

Enrollment and major protocol deviations will be listed and evaluated for their potential effects on the interpretation of study results. Protocol deviations related to covid-19 will

be tagged appropriately in the Protocol Deviation Management System (PDMS) and listed separately.

The distribution of patients based on the key strata of age at enrollment (<5, 5-11, ≥12), dialysis status (no dialysis, PD or HD) and previous ESA treatment (epoetin [epoetin alfa or epoetin beta or biosimilar] or darbepoetin alfa) will be summarized and compared by those who completed more than 20 weeks against those who did not.

### **4.3 EFFICACY ANALYSIS**

The primary efficacy endpoint is the change in Hb concentration (g/dL) between the baseline and the evaluation period for each patient. The analysis population for the primary and secondary efficacy analyses will be the ITT population consisting of all enrolled patients.

#### **4.3.1 Primary Efficacy Endpoint**

Hb concentration values (g/dL) over time and change in Hb from baseline to evaluation period will be presented in summary tables and graphically. The estimates will be summarized descriptively using means, standard deviation and percentiles.

The individual change from baseline will be reported using summary statistics (including mean, standard deviation and 90% CI of mean change). No formal statistical testing will be performed. Additional analysis will be performed by age category (<5, 5-11, ≥12 years), dialysis type (not yet on dialysis, PD, HD) and previous ESA (epoetin [epoetin alfa or epoetin beta or biosimilar] or darbepoetin alfa), if numbers allow.

The 90% confidence interval (CI) for the average per-patient Hb change from baseline to the evaluation period (weeks 17-21) will be calculated. If the lower limit of the CI is ≥-1 g/dL, the upper limit ≤1 g/dL and the number of dose increases and decreases are approximately balanced across the patients the conversion factor from prior ESA treatment for the first Mircera dose will be considered appropriate.

The Hb change from baseline is calculated on a per-patient basis, using an Area Under the Curve (AUC) approach to calculate an individual's average for both the baseline and evaluation periods and taking the difference. This per-patient change is then averaged over all patients and the confidence interval calculated.

The baseline period is defined as all assessments between the day of first study dose and the previous 35 days. If during the baseline period Hb measurements  $H_0, \dots, H_n$  are taken at timepoints  $t_0, \dots, t_n$ , a time adjusted average baseline Hb value will be calculated by

$$y = \frac{1}{2(t_n - t_0)} \sum_i (H_i + H_{i-1})(t_i - t_{i-1})$$

The value on the day of the first dose is included in the baseline calculation, as this assessment will be performed before the first dose is given.

The average Hb value for each individual during the evaluation period will be calculated using the same method as for the baseline period. The evaluation period is defined as all assessments between Visit 8 (Week 17) and Visit 10 (Week 21) inclusive. Subtracting the baseline period value from the evaluation period value gives the change in Hb concentration (g/dL) between the baseline and evaluation period.

For patients with no recorded Hb during the evaluation period, the primary endpoint will be missing. Values missing in between non-missing assessments will not be replaced or imputed. To correct for any increase in Hb caused by RBC transfusions, the Hb values measured within 3 weeks after an RBC transfusion will be deleted.

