4.3.2.1.1 Dose Adjustments of Mircera

Dose adjustments may be performed during the entire study. The dose of Mircera should be adjusted to maintain the individual patient's Hb within a target range of ± 1 g/dL of his or her baseline Hb and between 10.0–12.0 g/dL. Baseline Hb is calculated as the mean of Hb values obtained at Visit 1 (Week –3) and Visit 2 (Week –1).

Dose adjustments should be performed at the scheduled dosing days and should be based on the Hb value measured on that day. They should not be performed more often than once every 4 weeks.

Dose adjustment rules for Mircera in response to Hb changes, including those required for safety reasons, are summarized in [Table 3](#).

Table 3 Mircera Dose Adjustments

Hemoglobin Assessment	Compared with the Previous Mircera Dose
Hb decreases by more than 1.0 g/dL compared with baseline Hb.	Increase dose by approximately 25% (or closest higher PFS strength).
Hb is less than 10 g/dL and greater than or equal to 9 g/dL (Hb < 10.0 and ≥ 9.0 g/dL).	Increase dose by approximately 25% (or closest higher PFS strength).
Hb is less than 9 g/dL (Hb < 9.0 g/dL).	Increase dose by approximately 50% (or closest to 50% increase PFS strength).
Hb increases by more than 1.0 g/dL compared with the baseline Hb.	Decrease dose by approximately 25% (or closest lower PFS strength).
Hb is increasing and is approaching 12 g/dL or Hb is greater than or equal to 12 g/dL (Hb ≥ 12 g/dL).	Decrease dose by approximately 25% (or closest lower PFS strength).
If Hb exceeds 12 g/dL and continues to increase following a dose reduction.	Stop doses until Hb is less than 12.0 g/dL. Resume dose at approximately 25% below previous dose (or closest lower PFS strength) at next scheduled dosing day.

Hb = hemoglobin; PFS = *prefilled syringe*..

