6. STATISTICAL CONSIDERATIONS AND ANALYSIS PLAN

6.1 DETERMINATION OF SAMPLE SIZE

This is an exploratory study without a powered statistical group comparison. Therefore, no formal sample size estimation will be performed; however, the calculations below indicate the approximate precision that could be achieved.

Assuming a 30% withdrawal rate (based on the withdrawal rate for the NH19707 study), of the 40 patients evaluable for ITT and safety analysis, more than 26 patients will have data for the evaluation period. Twenty-six patients will be sufficient to provide approximately 90% power that the 90% CI for the Hb change from baseline to the evaluation period is between -1 and 1 g/dL, provided the standard deviation is smaller than 1.5 and the optimum dose conversion is able to maintain the Hb at the baseline level.

Approximately 10–15 of the patients will be < 12 years old, with the objective to include as many patients < 5 years old (minimum 3 patients) as possible. Approximately 10–15 patients, irrespective of their age, will not be on dialysis. Available HD patients receiving their ESA subcutaneously are eligible for enrollment. No more than 10 patients on HD should be enrolled.

To achieve the recruitment of the intended number of patients and in case of excessive dropout rate, additional patients may be enrolled to replace patients not treated for a minimum duration of 18 weeks.

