Appendix 1 Schedule of Activities Core Period (Week –3 to Week 21)

Study Period	Screening Period ~ 3 weeks ^a		Dose Titration Period 16 weeks					Evaluation Period 4 weeks		
	1	2	3	4	5	6	7	8	9	10
Visit Number										
Name of the Visit Day (start of Week ...) ^b	Week –3 ^a	Week –1 ^a	Week 1 ^c	Week 3	Week 5	Week 9	Week 13	Week 17	Week 19	Week 21 Follow-Up Visit ^d
Informed consent	x									
Medical history ^e	x									
Physical examination ^f	x									x
Pregnancy test ^g	x									
Vital signs, weight ^h	x	x	x		x	x	x	x		x
Height			x							x
Hematology ⁱ	x	x	x	x	x	x	x	x	x	x
Serum creatinine ^j	x		x							x
Iron parameters ^k	x	x				x		x		x
Kt/V for patients on PD	x									x
Kt/V or URR for patients on HD	x		x		x	x	x	x		x
Safety laboratory ^l	x					x				x
Anti-EPO and anti-Mircera antibody ^m			x			x				x
Injection pain questionnaire ⁿ	(x) ^o	(x) ^o	x			x				
Concomitant therapy ^p	Recorded throughout screening, dose titration and evaluation periods									

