## **1. BACKGROUND**

The NH19708 study is a pediatric study in patients aged 3 months to 17 years. It is an open-label, single-arm, multi-center study of Mircera administered once every 4 weeks subcutaneously (SC) for the maintenance treatment of anemia in pediatric patients with Chronic Kidney Disease (CKD). This study is the first use of Mircera in children under 6 years of age, and addresses the questions about SC administration of Mircera, its use in patients on PD or not yet on dialysis, and confirmation of the results of the modeling and simulation studies.

The main objective of the study is to ascertain the starting dose for the SC administration of Mircera for the maintenance treatment of anemia in pediatric patients with CKD on dialysis or not yet on dialysis when switching from stable SC maintenance treatment with epoetin [epoetin alfa or epoetin beta or biosimilar] or darbepoetin alfa.

This analysis plan covers the proposed methods for the final analysis following the database lock at the end of the study.

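### The Weeks 17–21 Hb interval in the SAP 4.3.1 rule mainly shows maintenance under titration, so judging the starting dose rests on a dose-balance clause that has no threshold and pools two conversion factors

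*SAP*

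**What the plan says.** - **Objective.** SAP 1: "The main objective of the study is to ascertain the starting dose for the SC administration of Mircera".
- **Rule.** SAP 4.3.1: "The 90% confidence interval (CI) for the average per-patient Hb change from baseline to the evaluation period (weeks 17-21) will be calculated". The first-dose conversion factor is called appropriate on two conditions, which open as follows: "If the lower limit of the CI is ≥-1 g/dL, the upper limit ≤1 g/dL and the number of dose increases and decreases". Those two counts have only to be roughly even over the patients. No number is attached to the second condition there or in SAP 4.3.2.2.
- **Titration.** Under Protocol 4.3.2.1.1 the dose "should be adjusted to maintain the individual patient's Hb within a target range": 1 g/dL either side of the patient's own baseline, and 10–12 g/dL. Changes are made on dosing days, on that day's Hb, at most every 4 weeks.
- **Schedule.** Protocol Appendix 1 labels Visits 3 to 7 "Dose Titration Period 16 weeks". Core-study doses fall at Weeks 1, 5, 9, 13 and 17. Hb is also taken at Week 3 and, before the dose, at Week 5.
- **Two factors, one statement.** Protocol 3.3.1 gives one factor for darbepoetin (4 × weekly µg / 0.55) and one for epoetin (4 × weekly IU / 125). The SAP rule is applied once, pooled. Analysis by prior ESA depends on numbers and carries no criterion.
- **Dose ratio.** SAP 4.3.2.2 summarises the Week 1 to Week 17 dose ratio by mean, median, minimum and maximum. It plays no part in the rule.

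**The concern.** The question is whether the first dose was right, but the only numeric condition is read after the dose has been corrected. If a child starts too high, Hb rises, the dose is cut, and by Weeks 17–21 Hb may be back near baseline. The interval then reflects the titration rules as much as the conversion factor.

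That leaves the balance of increases and decreases as the part that can reveal a wrong start. It has no threshold, so the conclusion can be settled after the counts are seen. It gives a small step the same weight as a large one. It also adds up patients converted with two different factors, so one factor set too high can offset the other set too low. At stake is the study's main conclusion, a statement on a paediatric starting dose.

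**Working it through.** **1. The plan's own figure.** Protocol 6.1 and SAP 2.3: n = 26, SD 1.5, true change 0, 90% CI within ±1 g/dL, about 90% power ("Twenty-six patients will be sufficient to provide approximately 90% power").
- Normal form: 2Φ(√26/1.5 − 1.645) − 1 = 2Φ(1.754) − 1 = 0.921.
- Exact t form: 0.903.

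The figure reproduces. It assumes that the conversion already holds Hb at baseline, so it does not describe the rule when the dose is wrong.

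**2. What the interval tolerates.** The half-width is t × SD/√n, with t = 1.708 on 25 df: 0.50 g/dL at SD 1.5 and 0.34 at SD 1.0. An observed mean shift of up to 0.50 or 0.66 g/dL passes.

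**3. Timing.** Changes at Weeks 5, 9 and 13 precede the window. A fourth may fall at Week 17, after that day's Hb sample. With equal spacing the trapezoid weights for Weeks 17, 19 and 21 are 1/4, 1/2 and 1/4, so 75% of the average comes after the Week 17 dosing day.

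**4. Reach of titration.** Three nominal 25% steps give 1.25³ = 1.95 upward or 0.75³ = 0.42 downward. Single syringe steps range from +20% (100 to 120 µg) to +67% (30 to 50) and from −17% (120 to 100) to −40% (50 to 30). A count treats them alike.

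**5. Simulation, set A.** The documents give no Hb dynamics, so these inputs are assumptions:
- n = 26, Table 2 starting doses, syringe strengths and Table 3 rules at Weeks 5, 9, 13 and 17.
- Red-cell life-span 60–110 days, or first-order turnover 40–80 days.
- Steady-state Hb 1–3 g/dL per dose doubling.
- Patient log-dose error SD 0.4; visit noise SD 0.5 and drift SD 0.5 g/dL.
- Median prior epoetin dose 3500 IU/week (both models) or 1500 (turnover only).

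One scenario (turnover 60 days, 2 g/dL per doubling, 1500 IU/week):

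| Start ÷ need | CI part passes, titrated (mean change) | CI part passes, dose unchanged (mean change) | Mean increases / decreases | Whole rule at ≤1.5:1 | at ≤2:1 |
|---|---|---|---|---|---|
| 0.5 | 0.70 (−0.63) | 0.00 (−1.64) | 52.8 / 2.7 | 0.00 | 0.00 |
| 0.67 | 0.99 (−0.33) | 0.09 (−0.91) | 36.9 / 5.7 | 0.00 | 0.00 |
| 1 | 1.00 (+0.04) | 0.95 (+0.10) | 19.0 / 12.8 | 0.50 | 0.77 |
| 1.5 | 0.99 (+0.33) | 0.03 (+1.11) | 8.8 / 23.6 | 0.07 | 0.24 |
| 2 | 0.89 (+0.50) | 0.00 (+1.81) | 5.6 / 31.4 | 0.00 | 0.00 |

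The ratios 1.5:1 and 2:1 are my readings of the balance clause. The choice moves the pass rate for an exact factor from 0.50 to 0.77.

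Ranges over set A for the CI part, titrated: 0.83–1.00 at 1.5 times, 0.33–1.00 at twice, 0.04–1.00 at 0.67 and 0.00–0.98 at half. A slower case (life-span 80 days, 2 g/dL per doubling) passes 1.00 at twice, 0.64 at 0.67 and 0.04 at half.

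**6. Other assumption sets for the CI part.**
- Set B (n = 26, turnover 40–80 days, 1–3 g/dL per doubling): 98–100% at 1.5 times, 90–100% at twice, 5–92% at half.
- Set C (n = 26, life-span 60–110 or turnover 40–60 days, 1.5–3 g/dL per doubling, omitting the Table 3 lines on Hb approaching 12 g/dL and on stopping): 0.33–1.00 at 1.5 times, 0.00–1.00 at twice, 0.55–1.00 at 0.67.

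**7. Whole rule, balance read as ≤2:1.**
- Set A, turnover models: 0.03–0.63 at 1.5 times, 0.00–0.19 at twice, 0.00–0.17 at 0.67, 0.71–0.89 with the correct dose.
- Set B: 0–7% at 1.5 times, 0% at twice, 0–18% at 0.67.
- Opposite errors (in set A, half the patients at 1.5–2 times and half at 0.5–0.67): 0.91–0.95 in set A, 82–98% in set B.

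**8. What unused data show.**
- Dose ratio, set C: the 90% CI for the geometric mean excluded 1 in at least 98% of trials at 0.5, 0.67, 1.5 and 2 times, against 3–15% with an exact factor.
- Dose ratio by prior ESA, set B: opposite errors were flagged in 75–100% of trials, with 13–22% false flags. Two separate 90% intervals, each read against 1, would give about 1 − 0.9² = 0.19.
- Week 5 Hb, set C: the interval excluded zero in 87–100% at 2 or 0.5 times and 57–100% at 1.5 or 0.67. Against a ±1 g/dL margin it is weak: in the life-span 80-day case it still passes 0.96 at twice the need.

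**The case against.** The strongest reply is that the rule already has a part aimed at this problem. A wrong start corrected by titration leaves lopsided dose changes. With a quicker Hb response (28 patients, time constant 30–60 days, 30% scatter), a doubled start produced 41–60 decreases against 3–10 increases per trial. Read as at most 2:1, the whole rule then passed in 0% of trials at 0.5, 0.67, 1.5 and 2 times, and in 88–98% when the factor was right. This stands. A reader might infer that the SAP would call a far-off starting dose appropriate. The documents do not support that, because the interval is only half of the rule. What the reply cannot supply is the threshold, and it fails when the two factors err in opposite directions.

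A reader might also infer that the interval passes whatever the starting dose, since titration aims at the same ±1 g/dL. That goes too far. The number is the same, but one is a band for each patient's Hb and the other bounds a CI for the mean. Under-dosing often fails with slow Hb dynamics, and only three changes precede the window.

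Two further replies have force. The study is exploratory with no formal testing, yet SAP 4.3.1 still attaches a conclusion to the rule. Hb over time, dose ratios and patients with dose changes are already reported, so only their role in the conclusion would change. That makes the fix cheap.

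**Conclusion.** The concern holds in a limited form. The Weeks 17–21 interval shows maintenance under titration. It often passes when the starting dose is wrong, most consistently when it is moderately too high: at 1.5 times the need, at least 0.83 in set A and 98% in set B, though as low as 0.33 in set C. For under-dosing the result runs from almost never to almost always. These are ranges under assumed Hb dynamics, not estimates for this trial.

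Detection of a wrong start therefore rests on the balance clause. If enforced at about 2:1, that clause catches most large errors in one direction. As written it has no number, ignores step size and lets opposite errors in the epoetin and darbepoetin factors cancel. These three gaps follow from the text and do not depend on the simulations.

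**What to change.** In SAP 4.3.1, before database lock:

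1. State that the Weeks 17–21 interval alone shows maintenance under titration and does not by itself support the conversion factor. Keep the primary endpoint.
2. Replace the balance of counts with the geometric mean Week 17/Week 1 dose ratio and its 90% CI, overall and separately for prior epoetin and prior darbepoetin. The sponsor should pre-specify the limits. Use the geometric mean because one doubling and one halving average to (2 + 0.5)/2 = 1.25 arithmetically but √(2 × 0.5) = 1 geometrically. The split by ESA is essential, since the overall ratio also cancels opposite errors.
3. State how a dose withheld at Week 17 (no logarithm exists for zero) and a patient who withdrew earlier are counted. Withheld doses come mainly from patients whose Hb ran high, so dropping them would bias the ratio.
4. Report the mean Week 5 pre-dose Hb change with 90% CI as evidence of direction only, not against ±1 g/dL, because Hb is not yet at steady state.

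**Cost.** SAP wording and a few summary rows from data already collected; no new visits, samples, patients or dosing rules. The conclusion becomes harder to meet and the by-ESA intervals are wide. If the log ratio had SD 0.4 (an assumption), the 90% limits would be the estimate times or divided by exp(1.708 × 0.4/√26) = 1.14 for 26 patients, exp(1.782 × 0.4/√13) = 1.22 for 13, and exp(2.132 × 0.4/√5) = 1.46 for 5.
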